7.3. Selection of Doses in the Study

PH94B is a Phase 2 investigational new drug that has shown statistically significant efficacy, rapid onset of effect, and an excellent safety profile in the treatment of performance anxiety and social interaction anxiety in subjects diagnosed with SAD. A formulation has been used with the i.n. administration route in Phase 1 and Phase 2 clinical studies. The i.n. route of administration is required in order for the small quantities of PH94B to engage directly with nasal chemosensory neurons interspersed in the nasal olfactory epithelium.

Nonclinical and clinical studies with PH94B are summarized in the Investigator's Brochure. Nonclinical and clinical data have shown that PH94B is safe for use in human subjects at increasing doses up to PH94B could not be quantified in blood samples of human subjects administered i.n. in a Phase 1 trial. No SAEs associated with the administration of PH94B have been observed in any clinical study to date. To date, the safety margin-based no-observed-adverse-effect level from toxicity levels have indicated that the proposed doses are safe. The profile of physiological and behavioral responses to PH94B was similar for males and females, proposes the self-administration of a single dose of PH94B, 3.2 µg (one 1.6 µg spray per nostril), for males and females, based on Phase 1 and Phase 2 study outcomes in general, and in particular on the observations made in study The IP (PH94B or placebo) will be parallel group fashion during a clinic-based public self-administered i.n. once in a speaking challenge. Subjects will be randomly assigned to treatment with either PH94B or placebo.

7.4. Study Sites

The study will take place at approximately 15 to 18 sites in the United States. Each site is anticipated to screen a sufficient number of subjects to randomize approximately 14 subjects. A study site with a high recruitment rate may be allowed to recruit more subjects if other sites have slow enrollment.

AD-MW-07.08 18-Jun-2019 Page 30 of 101

7.5. End of Study Definition

A clinical trial is considered completed when the last subject's last study visit has occurred.

12-Aug-2022 Amendment 3, Version 4.0 AD-MW-07.08 18-Jun-2019 Page 31 of 101

8. SUBJECT POPULATION

8.1. Selection of Study Population

Eligibility for participation in the study will be determined from demographic information, medical and psychiatric history, physical and psychiatric examination, ECG, clinical laboratory findings, and clinical rating scale assessments performed at Screening (Visit 1). Subjects may be recruited from the Investigator or sub-Investigator clinical practices, the center's existing database, referring physicians, or direct advertisement or other lead generation source. Any information to be disseminated to potential subjects (handouts, brochures, etc.), as well as direct advertisements, including direct electronic or digital advertising, must be approved by VistaGen and by the IRB prior to use and implementation.

8.2. Study Entry Criteria

Subjects who do not meet all of the eligibility criteria will not be enrolled.

8.2.1 Inclusion Criteria

To be considered eligible to participate in the study, a subject must meet the following inclusion criteria:

- 1. Written informed consent provided prior to conducting any study-specific assessment.
- 2. Male and female adults, 18 through 65 years of age, inclusive.
- 3. Current diagnosis of SAD as defined in the Diagnostic and Statistical Manual of Mental Disorders, 5th Edition, and confirmed by the MINI.
- 4. Clinician-rated LSAS total score ≥70 at Screening (Visit 1).
- 5. Clinician-rated Hamilton Depression Score 17-items total score <18 at Screening (Visit 1).
- 6. Women of childbearing-potential must be able to commit to the consistent and correct use of an effective method of birth control throughout the study and must also have a negative urine pregnancy test result at both Screening (Visit 1) and Baseline (Visit 2), prior to IP administration. Effective methods of contraception include: condoms with spermicide, diaphragm with spermicide, hormonal contraceptive agents (oral, transdermal, or injectable), or implantable contraceptive devices.
- 7. Negative COVID-19 test for subjects with COVID-19 symptoms or those who have had direct exposure to someone with a positive COVID-19 test, and/or completion of quarantine period consistent with requirements at the study site as determined by the Investigator.

AD-MW-07.08 18-Jun-2019 Page 32 of 101

8.2.2 Exclusion Criteria

To be considered eligible for entry into the study, a subject must not meet any of the following exclusion criteria:

- 1. Any history of bipolar disorder (I or II), schizophrenia, schizoaffective disorder, psychosis, anorexia or bulimia, premenstrual dysphoric disorder, autism-spectrum disorder, or obsessive-compulsive disorder.
 - Any other current Axis I disorder, other than SAD, which is the primary focus of treatment. Note that subjects with concurrent Generalized Anxiety Disorder are eligible for the study provided that Generalized Anxiety Disorder is not the primary diagnosis.
- 2. Subjects who meet criteria for moderate or severe alcohol or substance use disorder within the 1 year prior to Study entry.
- 3. In the opinion of the investigator, the subject has a significant risk for suicidal behavior during the course of their participation in the study, or
 - a. At Screening (Visit 1): the subject scores "yes" on items 4 or 5 in the Suicidal Ideation section of the Columbia-Suicide Severity Rating Scale (C-SSRS) with reference to a 6-month period prior to screening; or
 - b. At Screening (Visit 1): the subject has had 1 or more suicidal attempts with reference to a 2-year period prior to screening; or
 - c. At Baseline (Visit 2): the subject scores "yes" on items 4 or 5 in the Suicidal Ideation section of the C-SSRS with reference to screening; or
 - d. The subject is considered to be an imminent danger to themself or others.
- 4. Clinically significant nasal pathology or history of significant nasal trauma, nasal surgery, total anosmia, or nasal septum perforation that may have damaged the nasal chemosensory epithelium.
- 5. An acute or chronic condition, including an infectious illness, uncontrolled seasonal allergies at the time of the study, or significant nasal congestion that potentially could affect drug delivery to the nasal chemosensory epithelium.
- 6. Two or more documented failed treatment trials with a registered medication approved for SAD, at any time during the lifetime of the subject, whereby an adequate treatment trial is defined as that described in the package insert for a particular drug during which the subject received an adequate medication dosage (defined as the treatment dose indicated in the package insert to obtain efficacy for that particular drug).
- 7. Use of any psychotropic medication within 30 days before study entry (other than medication permitted for insomnia: eszopiclone, ramelteon, melatonin, zaleplon, zolpidem, or antihistamines).
- 8. Use of any anxiolytics, such as benzodiazepines or unapproved treatments such as beta blockers, within 30 days before study entry; concomitant use is prohibited during the study. Subjects who have been taking benzodiazepines daily for 1 month or longer at the time of Visit 1 are not eligible to participate.

Amendment 3, Version 4.0

AD-MW-07.08 18-Jun-2019 Page 33 of 101

- 9. Use of any over-the-counter product, prescription product, or herbal preparation for treatment of the symptoms of anxiety or social anxiety within 30 days before study entry; concomitant use is prohibited during the study.
- 10. Prior participation in a clinical trial involving PH94B.
- 11. Women who have a positive urine pregnancy test prior to IP administration. Women who are currently breastfeeding are not eligible unless they are willing to stop breastfeeding for the duration of time between Visit 2 and Visit 4.
- 12. Subjects with clinically significant abnormalities in hematology, blood chemistry, urinalysis, electrocardiogram, or physical examination identified at the Screening visit or Baseline visit that in the clinical judgment of the Investigator, could place the subject at undue risk, interfere with study participation, or confound the results of the study.
- 13. Subjects with a positive urine drug screen at either Screening (Visit 1) or Baseline (Visit 2)
- 14. Any current clinically significant and/or uncontrolled medical condition, based on medical history or as evidenced in screening assessments, such as COVID-19, HIV, cancer, stroke, congestive heart failure, uncontrolled diabetes mellitus, or any other medical condition or disease that, in the clinical judgment of the Investigator, could place the subject at undue risk, interfere with study participation, or confound the results of the study.
- 15. History of cancer or malignant tumor not in remission for at least 2 years. Basal cell skin cancers are not exclusionary.

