10.2.1 Screening and Washout

10.2.1.1 Screening (Visit 1)

Screening begins after the written informed consent has been obtained. The purpose of the screening phase is to:

- Ensure that appropriate subjects are entered into the trial
- Determine that the subject meets all eligibility criteria
- Collect demographic and medical data permitting characterization of the subject
- Ensure that prohibited medications are discontinued and
- Determine that subjects are willing to undertake up to 2 anxiety-provoking situations at the site

To meet these objectives, the duration of screening must be tailored to the individual subject and may last from a minimum of 3 to a maximum of 35 days. Subjects continuing to meet all eligibility requirements at Baseline (Visit 2) will undergo a Visit 2 public speaking challenge (APPENDIX B).

AD-MW-07.08 18-Jun-2019 Page 40 of 101

Generally, healthy subjects who are thought to meet inclusion and exclusion criteria and express an interest in participating will be informed about the study, the investigational product (PH94B and placebo), required visits and scheduling, and asked whether they wish to participate. All subjects agreeing to participate must give written informed consent using the IRB-approved ICF before any study-related procedures are performed (including tapering of prohibited medications). The ICF will be signed and dated by the subject and Investigator or other appropriate site staff, and a copy of the signed ICF will be given to the subject. The informed consent process will be documented in the source records for each subject.

After the ICF process is complete, a subject number will be allocated by the site, by assigning the next sequential subject number available. Subject numbers will be 4-digit numbers beginning with the site number. Subject numbers will not be sex-specific and will be assigned sequentially in the order in which the ICF is signed.

Screening, which is to occur at least 3 days, but no more than Visit 2:

35 days prior to Visit 2:

- 1. ICF will be reviewed and completed before any other assessments. Collect demographic information; and assign subject number
- 2. Urine sample for drug screen and pregnancy test (if appropriate) will be collected early in the screening visit to determine eligibility and to guide diagnostic interviews, especially with regards to substance use assessment. The urine sampling is to include:

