10.2.2 Visit 2 (Baseline): Public Speaking Challenge

For subjects continuing to meet all eligibility criteria, the following Visit 2 assessments will be completed:

- Measure vital signs after the subject has rested for 5 minutes: seated systolic and diastolic blood pressure, heart rate, respiratory rate, and body temperature
- Obtain urine sample for urine drug screen: Instant Exam to be performed on site, with results thoroughly documented in the source; urine sample to be sent to central laboratory for confirmation if on-site screen is positive
- For females of child-bearing potential, obtain urine sample and complete on-site urine pregnancy test
- Record concomitant medication use including the completion of any washout
- Review all inclusion and exclusion criteria

For subjects meeting all study inclusion criteria and no study exclusion criteria, the following Visit 2 procedures will be performed:

- Introduce the self-rated anxiety scale, the SUDS, to the subject and review the descriptions of the various SUDS scores (APPENDIX A)
- Dispense and instruct subject to self-administer IP
- The subject will be returned to a waiting area after IP dosing
- the subject will be informed that they must give a 5-minute speech to a live audience of

Amendment 3, Version 4.0

AD-MW-07.08 18-Jun-2019 Page 43 of 101

Protocol PH94B-CL032

- The subject will be escorted into a room to give a 5-minute speech in front of after the last SUDS anticipatory anxiety score is collected.

 At these timepoints,
- the subject will be given information on attending the next visit (Visit 3) otherwise, the subject will complete the remaining assessments for Visit 2, will not be randomized, and will be discharged from the study
- If the subject cannot complete the speech during the performance phase due to anxiety levels, the SUDS level will be requested from them before they leave the room and all remaining time points will be marked as not done
- Record any AEs reported
- Administer C-SSRS (Since Last Visit) as the last part of Visit 2

For the subjects attending the next visit (Visit 3), it will be scheduled 1 week (± 2 days) after the date of Visit 2.

12-Aug-2022 Amendment 3, Version 4.0
AD-MW-07.08 18-Jun-2019 Page 44 of 101

12-Aug-2022 Amendment 3, Version 4.0
AD-MW-07.08 18-Jun-2019 Page 45 of 101

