3.7. Schedule of Events

The timing of all study assessments is outlined in the Schedule of Events (Table 1) below.

Table 1: Schedule of Events

Assessment	Screening Day -35 to -3 Visit 1	Baseline Day 0 Visit 2	Treatment Day 7 Visit 3	Follow-Up Day 14 Visit 4
Written Informed Consent	X		⇒	
Subject Demographics	X			
Urine Drug Screen (Instant Exam, on site)	X	X	X	X
Urine Pregnancy Test	X	X	X	X
MINI	X			
Medical and Psychiatric History	X			
Prior and Concomitant Medication Recording	X	X	Х	х
n				
LSAS	X			X

AD-ST-33.06 Effective date: 12-Nov-2020

Assessment	Screening Day -35 to -3 Visit 1	Baseline Day 0 Visit 2	Treatment Day 7 Visit 3	Follow-Up Day 14 Visit 4
Hamilton Depression Scale	X			X
C-SSRS	X	X (end of visit)c	X (end of visit)c	X
Physical Examination and Examination of Nasal Passages	X			X
Vital Signs	X	X	X	X
Electrocardiogram	X			X
Blood Tests and Urinalysis	X			X
Inclusion/Exclusion Review	X	X		
Investigational Product Administration Training	X			
SUDS Introductiona		X		
Investigational Product Administration		x	X	
Public Speaking Challenge ^b		X	X	
Randomization			X	8
PGI-C Scale				8 .
CGI-I Scale			X	
Adverse Events Recording		X	X	X

Abbreviations: C-SSRS = Columbia Suicide Severity Rating Scale; CGI-I = Clinical Global Impression of Improvement; LSAS = Liebowitz Social Anxiety Scale; MINI = Mini-International Neuropsychiatric Interview; PGI-C= Patient Global Impression of Change; SUDS = Subjective Units of Distress Scale

- Introduce the SUDS to the subject and provide scores in relation to feelings of distress (see protocol).
- b. Public Speaking Challenge involves the collection of SUDS scores from the subject and is outlined in the protocol.
- c. The C-SSRS at Visits 2 and 3 should be administered at the end of the visit, i.e., after investigational product administration and public speaking challenge.

4. Statistical Analysis and Reporting

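### Exclusion 3c is not consistent with the Visit 2 order: all criteria must be cleared before the placebo dose and speech, but the C-SSRS that 3c needs comes last

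*Protocol*

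**What the plan says.** **The criterion.** Protocol Section 8.2.2, exclusion 3c, applies at Baseline (Visit 2). It excludes a subject with a yes on item 4 or 5 "in the Suicidal Ideation section of the C-SSRS with reference to screening".

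**The gate before the speech.** Section 10.2.1.1 states: "Subjects continuing to meet all eligibility requirements at Baseline (Visit 2) will undergo a Visit 2 public speaking challenge". In Section 10.2.2 the pre-dose list is vital signs, urine drug screen, pregnancy test and concomitant medication, ending with "Review all inclusion and exclusion criteria". The list containing the dose and speech then opens with "For subjects meeting all study inclusion criteria and no study exclusion criteria, the following Visit 2 procedures will be performed".

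**The timing of the C-SSRS.** The closing step of Section 10.2.2 is "Administer C-SSRS (Since Last Visit) as the last part of Visit 2". Protocol Table 2-1 marks the Visit 2 C-SSRS as end of visit. SAP Table 1, footnote c, says that at Visits 2 and 3 the scale "should be administered at the end of the visit, i.e., after investigational product administration and public speaking challenge".

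**Randomisation.** This takes place at Visit 3. Protocol Section 9.5 and SAP 3.5 both limit it to subjects who meet the entry criteria and complete the Visit 2 challenge. SAP 3.5 adds that at least one SUDS score at that challenge must be 75 or higher.

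**The concern.** The protocol makes clearance on every criterion a condition of the Visit 2 dose and speech. For 3c, the only scheduled source of data does not exist until both are over.

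A site that follows the stated order exactly would take a subject with new item 4 or 5 ideation (active ideation with some intent, or with plan and intent) through a provoked-anxiety procedure. The protocol reserves that procedure for subjects who meet no exclusion criterion. The site would learn of the conflict only afterwards. SAP 7.2 lists breaches of entry criteria among important deviations, so a site could face that classification for doing what the procedure list says.

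**Working it through.** No formula applies. The check sets the order of procedures against what each criterion needs.

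**1. Visit 2 order as written (Section 10.2.2).** Vital signs, drug screen, pregnancy test and concomitant medication come first. Then come the review of all criteria, SUDS introduction, dose, waiting area, 5-minute speech, AE recording and C-SSRS.

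**2. Criteria that rest on a scheduled Visit 2 test.**

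| Criterion | Test | Position relative to the review |
|---|---|---|
| Inclusion 6, exclusion 11 | Pregnancy test | Before |
| Exclusion 13 | Drug screen | Before |
| Exclusion 3c | C-SSRS items 4 and 5 | After the review, dose and speech |

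Only 3c is out of order.

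**3. Is this a gap in the published text?** No. Three visible statements agree on the late timing: Section 10.2.2, Table 2-1 and SAP Table 1 footnote c. Two visible statements set the earlier gate: Sections 10.2.1.1 and 10.2.2.

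**4. Can 3c still act later?** Yes. Visit 3 is 7 ± 2 days after Visit 2, so the result is available 7 − 2 = 5 to 7 + 2 = 9 days before randomisation. Section 9.5 and SAP 3.5 then require the entry criteria to be met.

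**5. What is the exposure before 3c is known?** SAP 7.4 says every Visit 2 vial contains placebo. The exposure is therefore a placebo spray and one 5-minute speech, with no PH94B.

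**6. What covers the risk meanwhile?** At Screening, HAM-D must be below 18, 3a excludes item 4 or 5 ideation in the prior 6 months, and 3b excludes an attempt in the prior 2 years. At the Visit 2 review, the investigator-opinion part of exclusion 3 and item 3d (imminent danger) can be applied before the dose. None of these is a structured rating of the 3 to 35 days since Screening.

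**7. How many subjects?** The plan is to screen about 400 and randomise 208, so the number reaching Visit 2 lies between those figures. The documents give no rate of new item 4 or 5 responses between Screening and Visit 2. Any count would rest wholly on an assumed rate, so none is given here.

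**The case against.** The best defence is that 3c is meant to gate randomisation only.

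- 3c says Visit 2 without saying before dosing. Inclusion 6, by contrast, asks for a "negative urine pregnancy test result at both Screening (Visit 1) and Baseline (Visit 2), prior to IP administration". A rating at the end of Visit 2 is still a Visit 2 rating.
- SAP 3.5 already makes randomisation depend on a SUDS score of 75 or higher at the Visit 2 challenge, which can be known only after the placebo dose and speech. Qualification after the speech is therefore part of the design.
- A rating after the stressor also has safety value, because it captures ideation arising during the visit.

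Much of this stands. It rules out two stronger readings that a reader might infer. One is that 3c can never be applied, so that a subject with new intent-level ideation could properly go on to PH94B. Section 9.5 and SAP 3.5 do not support that. The other is that the protocol forgot to check the C-SSRS before randomising. The visible steps in Section 10.2.3 show no such check, but part of the condition for going on to Visit 3 is blanked in Section 10.2.2, so its absence cannot be counted as an omission.

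The defence does not remove the conflict. Section 8.2.2 ties the exclusions to study entry, and Section 10.2.1.2, writing about washout, treats Visit 2 as study entry. Even if 3c gates randomisation only, Section 10.2.1.1 still demands *all* requirements before the speech, and Section 10.2.2 allows no exception.

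**Conclusion.** The inconsistency is real and should be corrected. As written, the Visit 2 review cannot include 3c, although Sections 10.2.1.1 and 10.2.2 require it to.

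The consequence is modest: a placebo dose and one anxiety-provoking speech for a subject who should not have had them, with partial cover from clinical judgement and 3d. Exposure to PH94B can still be prevented. That few subjects would be affected is a judgement based on the Screening exclusions and the short interval, since the documents give no rate. Sample size, power, type I error and the efficacy analysis are unaffected.

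The conclusion rests only on visible text and does not depend on which gate the sponsor intended, because the wording needs correcting either way.

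**What to change.** **Preferred.** Give the C-SSRS (Since Last Visit) before the Visit 2 criteria review and keep the end-of-visit rating for safety. Amend Section 10.2.2, Table 2-1 and SAP Table 1 footnote c to match. Because Visit 2 would then hold two ratings, the SAP needs a rule: the pre-dose rating serves 3c only, and the end-of-visit rating feeds the by-visit table (14.3.6.5) and the treatment-emergent summaries. State the reference period of each form. The C-SSRS baseline in SAP Table 2 (Visit 1) can stay.

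The cost is one extra short interview per subject with a scale already in use. It precedes the Visit 2 speech but not the Visit 3 speech, so the two challenge visits become slightly less alike. That applies equally to both arms, because randomisation comes later.

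**If 3c is meant to gate randomisation only.** Say so in 3c, except it from the all-criteria wording in Sections 10.2.1.1 and 10.2.2, and add a line in Section 10.2.3 confirming the end-of-Visit-2 C-SSRS result before the randomisation step. This changes wording only and uses a result already collected, but it leaves the speech without a structured ideation check beforehand.

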8.3. Premature Subject Withdrawal

12-Aug-2022

A subject will be considered to have completed the Study when he or she completes Visit 4.

All subjects will be advised that they are free to withdraw from participation in this study at any time, for any reason, and without prejudice. The investigator should make every reasonable attempt to keep subjects in the study; however, subjects must be withdrawn from the study if they withdraw consent to participate. Investigators must attempt to contact subjects who fail to attend scheduled visits by telephone or other means to exclude the possibility of an AE being the cause of withdrawal. Should this be the cause, the AE must be documented, reported, and followed as described in Section 11.2.

The sponsor reserves the right to request the withdrawal of a subject due to protocol deviations or other reasons.

The investigator also has the right to withdraw subjects from the study at any time for the following reasons:

- Any AE, laboratory abnormality, or concomitant illness which, in the opinion of the Investigator, indicates that continued treatment with IP or any other aspect of the study is not in the best interest of the subject
- Disease progression that, in the Investigator's opinion, precludes the subject's continued participation in the study
- Significant non-compliance with the requirements of the protocol or treatment

AD-MW-07.08 18-Jun-2019 Page 34 of 101

- The subject requires a medication prohibited by the protocol
- Termination of the Study by VistaGen
- At the discretion of the Investigator or VistaGen
- Pregnancy

If a subject is withdrawn before completing the study, the reason for withdrawal and the date of discontinuation will be recorded on the appropriate page of the electronic case report form (eCRF). Whenever possible and reasonable, the evaluations that were to be conducted at the completion of the study should be performed at the time of premature discontinuation.

All attempts will be made to have subjects return to the study center to complete Visit 4 in the event of early withdrawal from Visit 3 after IP administration. All attempts, including phone or email, to contact the subject must be recorded in the source documents. If the subject fails to respond to those methods, a certified, return receipt letter must be sent to the subject's address indicating that they should contact the study center, with a copy retained in the source documents. Only if all of these attempts fail will it be deemed that the subject is in fact Lost to Follow-up and no final safety data can be collected.

Subjects who sign the ICF and are subsequently withdrawn will not be replaced.

